## **4.0 PATIENT ELIGIBILITY**

Subjects must meet all of the inclusion and exclusion criteria to be registered to the study. Study treatment may not begin until a subject is registered.

### **4.1 Inclusion Criteria**

1. All patients must be capable of giving written informed consent.
2. Male or female subjects of any race; between 18 to 60 years of age, inclusive.
3. No hospitalization other than for evaluation in the past four months
4. Resides in a stable living situation, according to the investigator's judgment.
5. Diagnosis of schizophrenia or schizoaffective disorder of at least one year duration, as established by the SCID-I, and verified with medical records and/or confirmation of diagnosis by treating clinician. The illness is in a nonacute phase as determined by the subject's primary treating clinician
6. Current psychotropic drug treatment consists of monotherapy with an atypical antipsychotic drug.
7. No more than a mild level of EPS as determined by the Simpson Angus Scale (SAS) total score:  $\leq 6$
8. Not taking anticholinergic medication for EPS
9. No evidence of tardive dyskinesia
10. Subjects healthy enough to complete a 9-week clinical trial
11. Women of childbearing potential must have a negative pregnancy test at screening and baseline, and agree to use adequate protection (i.e. double barrier method) for birth control.
12. Able to complete cognition assessments in English
13. General intellectual abilities falling broadly within the average estimated IQ  $\geq 80$ , as measured by the *Wide Range Achievement Test – 4th Edition (WRAT-IV)*.

### **4.2 Exclusion Criteria**

1. Failure to perform screening or baseline examinations
2. Hospitalization within 8 weeks before screening, or change of antipsychotic medication or dose within 2 months prior to screening
3. Subjects who have participated in another clinical trial with an experimental medication within the past 2 months.
4. Patient has had cognitive battery similar to those used in this study within the last 12months
5. Subjects with other DSM-V Axis I or Axis II primary diagnoses
6. Diagnosis of alcohol or substance abuse or dependence within the past 3months,
7. Significant suicide risk as determined by the Columbia Suicide Severity Rating Scale (C-SSRS)

8. Subjects who plan to begin a new course of cognitive remediation therapy, or have been receiving cognitive remediation therapy for less than one year.
9. History of myocardial infarction, unstable angina, uncontrolled hypotension or hypertension within 3 months before screening.
10. Clinically significant abnormality on screening ECG
11. Alanine transaminase (ALT) or aspartate transaminase (AST) > 2.5 times the upper limit of normal (ULN)
12. History of stroke, brain tumor, head trauma with loss of consciousness, or other clinically significant neurological condition within 12 months before screening
13. Subjects with other uncontrolled medical conditions, in the opinion of the investigator
14. Polypharmacy with two or more antipsychotic drugs or mood stabilizers
15. Use of benzodiazepines
16. Individuals with kidney dysfunction will not be enrolled, as dysfunctional kidneys may have difficulty clearing the magnesium from the body
17. Individuals who are currently taking magnesium supplements

## 5.0 TREATMENT PLAN

### 5.1 Study Design

#### Design of Clinical Trial

After providing written informed consent and completing baseline assessments, patients with schizophrenia or schizoaffective disorder will be randomized to placebo or MMFS-202-302. We will make every effort to enroll subjects who have had a recent fMRI assessment as part of the Northwestern University Psychiatric Clinical Research Program. This would provide valuable pre-dose information regarding any structural abnormality. No patients with tardive dyskinesia will be admitted because of the evidence for its deleterious effect on cognition.

Patients will be recruited primarily from three mental health clinics in the Chicago area, at which the principal investigator been successfully recruiting for the last 28 months: the Stone Mental Health Center which is a part of the Northwestern Medicine system, Community Counseling Centers of Chicago (C4), and Clayton House, a residential treatment center. Other mental health facilities in the area will also be referral sources. We expect to recruit 4-5 patients per month for this study without difficulty. We expect the recruitment to be complete within 12 months or less after approval by the Northwestern University Institutional Review Board and study initiation.

All patients who are screened must provide written informed consent. Our lab has trained and certified coordinators and research assistants who will be assigned to this study as their primary responsibility. We have used the MATRICS cognitive battery in many studies over the last five years. Because of our 20- year interest in cognitive impairment in schizophrenia, there are a few other cognitive tests we collect on all of our research patients. These include a measure of phonemic verbal fluency (FAS), the Brown- Peterson Auditory Consonant Trigrams test of working memory (ACT), and the Wisconsin Card Sorting Test (WCST). We have experienced no difficulty in administering the MATRICS battery and this group of tests, which takes another 30 minutes to our patients.

We propose to study a total of 60 randomized participants, 30 receiving MMFS-202-302 and 30 randomized to placebo.

## 6.0 STUDY PROCEDURES

Study visits will include screening and 5 treatment visits (baseline, Weeks 1, 3, 6, and 9). Patients will be contacted by telephone at Weeks 2, 4, 5, 7, and 8 for monitoring of medication compliance, change in concomitant medication, and adverse events. Please see Appendix 1 – Schedule of Assessments.

At screening, the Structured Clinical Interview for Diagnosis for DSM Disorders (SCID) will be completed for confirmation of psychiatric diagnosis. A medical/psychiatric history will also be collected and a physical exam will be performed. Vital signs including weight, height, waist and hip measurement will be obtained at screening to record body mass index.

Subjects will be administered MMFS-202-302 at a fixed single dose of 2 grams (1 gram twice per day),

or placebo after the completion of the baseline assessments.

Methods:

- A) Measurement and Treatment Research to Improve Cognition in Schizophrenia (MATRICS) battery, including some supplemental cognitive assessments (FAS, ACT, WCST)
- B) Positive and Negative Syndrome Scale (PANSS) for schizophrenia and schizoaffective disorder
- C) MRI assessments:
  - a. Structure: MPRAGE (T1), T2
  - b. Function: Resting connectivity
  - c. Function: Reward/aversion and attention: fMRI paradigm of IAPS (standardized images selected to be neutral, pleasurable, or arousing) and Spinner Task
  - d. Function: Capacity working memory task
- D) A set of cognitive psychological paradigms performed outside of the magnet following the MRI scan:
  - a. Keypress task for an adaptation of the International Affective Picture Set (IAPS)
  - b. A spinner wheel rating task of the reward/aversion associated with monetary gains/losses
- E) Brief Negative Symptom Scale (BNSS)
- F) Calgary Depression Scale for Schizophrenia
- G) Clinical Global Impression of Severity (CGI-S) and Change (CGI-C)
- H) Measurement of RBC Mg at baseline and end of study
- I) EEG evaluation, measuring connectivity and activation using learning and memory tests

## 7.0 RANDOMIZATION METHOD

Those who meet the study inclusion criteria will be randomized into one of two treatment groups, one to receive adjunctive therapy of MMFS-202-302 and the other to receive placebo. Using SAS software, a computer-generated randomization sequences for each treatment arm will be assigned using permuted block method limiting imbalance in numbers between groups. To assign the randomization, the SAS procedure PROC PLAN will be used [19]. Until the trial is concluded, the randomization sequence will be blind to the study participants as well as research coordinators and raters. Randomization list will be provided by assigned statistician, [name], and will be held by unblinded study drug manager at [name].

## 8.0 STATISTICAL CONSIDERATIONS

### 8.1 Analysis of Clinical Data

Data will first be analyzed for efficacy on a per-protocol basis. The per-protocol population will include all subjects who complete all scheduled visits (+/- 5 days from planned visit time), have no protocol deviations that in the judgment of the principal investigator would invalidate their efficacy data, and achieve medication compliance of 80-120% (determined by pill counting; if pill packs are not available for confirmation, self-report of compliance will be used). Participants whose assessment falls +10 days or less from the scheduled visit will be included in per-protocol population, only if they were taking the study compound throughout. Data will secondarily be analyzed for efficacy on an intent-to-treat basis, with last observation carried forward (LOCF) for missing values or dropouts; subjects who did not receive any study compound will be excluded from the full analysis set, preserving the intent-to-treat principle. The primary analysis will be a univariate ANCOVA adjusting for baseline differences in the dependent measures of interest. We would also examine some variables categorically. The MATRICS working memory subscale T-score at 9 weeks will be the primary endpoint. Secondary endpoints will include the Clinical Global Impression of Change (CGI-C); the MCCB composite score; other individual cognitive domain subscale T-scores of the MCCB; a working memory composite score comprised of the 2 MCCB working memory subscale tests and the ACT test; and the PANSS positive and negative scales and BNSS. All endpoints will be evaluated as 9-weeks change from baseline, except for PANSS, which will be evaluated at both 6 and 9 weeks compared to baseline. Responder analyses will also be carried out using a chi-square test for the MCCB working memory subscale as a secondary endpoint evaluating clinical significance, using a cutoff of 0.5 standard deviation improvement (T-score improvement of  $\geq$  5 points). Finally, separate exploratory subgroup analyses will be performed on the MCCB working memory subscale T-score restricted to the subset of subjects who score 0, 0.5, or 1.0 SD or below the mean for normal age-matched normative data for that subscale. Analogous subgroup analyses will also be performed for the MCCB composite score, and the other MCCB subscale scores.

Alpha will be set at 0.05 for all analyses. The individual scores for each of the 6 other neuropsychological MCB subscales, and supplementary cognitive tests (ACT, WCST, FAS), as well as the CGI-C measure of functional change will be evaluated to provide supporting information for primary and secondary measures.

Assumptions for the power analysis included random assignment into one group receiving placebo and one MMFS-202-302. The MCB, as the primary instrument will be collected at baseline and at end point (9 weeks). Using univariate ANCOVA with baseline score as covariate, the time average difference in the response variable will be compared between groups to detect treatment difference. Based on Javitt et al, 2012, we assume the mean baseline working memory score will be 36.4, SD 11.7 for both groups. We assume the placebo group will show no improvement with an SD of change of 6.5, while the treatment group will improve a mean of 5 points with the same SD of change, a medium effect. We assume the correlation coefficient of repeated observation to be 0.5 and the covariance structure to be compound symmetry. The power calculation was conducted with alpha level of 0.05. Full results are available upon request. With a two-sided test, the analysis reveals that 28 subjects per group are required assuming 5 points of improvement of the treatment group compared to the placebo for the desired power of 80% with alpha level of 0.05. We plan to recruit 30 per group to account for drop outs. Thus, allowing for attrition up to 20%, this sample size will provide 74-83% power to detect the hypothesized medium treatment effect.

We will assess MMFS-202-302 effects on negative and positive symptoms as additional endpoints, as measured by the BNSS and PANSS. Further, we will analyze the effect on drug tolerability as determined by the following: body weight, body mass index (BMI), waist circumference, and movement rating scales.

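### The leading efficacy analysis is per-protocol and can drop patients who have both MCCB scores, while the second-ranked intent-to-treat analysis turns a missing week-9 MCCB score into a zero change

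*Combined protocol and SAP*

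**What the plan says.** Section 8.1 sets the order of the efficacy analyses: "Data will first be analyzed for efficacy on a per-protocol basis", and then "Data will secondarily be analyzed for efficacy on an intent-to-treat basis, with last observation carried forward (LOCF) for missing values or dropouts". Patients who took no study compound are left out of the full analysis set. The model is given separately: "The primary analysis will be a univariate ANCOVA adjusting for baseline differences in the dependent measures of interest". That sentence names no population. Neither do the objectives (2.1), the primary endpoint (3.0) or the power paragraph (8.1).

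Per-protocol membership has three parts:

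- **Visits.** "The per-protocol population will include all subjects who complete all scheduled visits", within 5 days either way. An assessment up to 10 days late still counts if the patient was taking study compound throughout.
- **Compliance.** 80 to 120%, by pill count or, failing that, self-report.
- **Deviations.** Patients must "have no protocol deviations that in the judgment of the principal investigator would invalidate their efficacy data".

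The scheduled treatment visits are baseline and weeks 1, 3, 6 and 9 (6.0). The MCCB is given only at baseline and week 9 (8.1, 9.1.2, Appendix 1). The PANSS also has a week-6 assessment (9.1.3). When a patient stops treatment, follow-up is permitted (10.0). A final physical examination is requested at discontinuation (9.1.8), but no exit MCCB is scheduled.

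**The concern.** First and secondarily are the only ranking the plan gives. If the two analyses disagree, nothing else says which one answers the primary question, and the order points to per-protocol.

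All three membership rules act after randomisation. They can remove a patient whose primary endpoint is fully observed, for instance one who missed the week-3 visit but completed both MCCB sessions. If such exclusions are related to outcome and differ between arms, the comparison loses the protection of randomisation, and the bias can go either way. One rule rests on judgment, and no text says that membership is fixed before unblinding.

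The intent-to-treat analysis is a weak fallback for this endpoint. With a single post-baseline MCCB, the only earlier value to carry forward is the baseline score. A missing week-9 score becomes a change of exactly zero and, under the same rule, a non-responder at the 5-point cutoff.

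**Working it through.** **Inputs from 8.1:** 30 per group; placebo change 0; MMFS change 5; SD of change 6.5; two-sided alpha 0.05; attrition up to 20%. For the simulations, baseline SD 11.7, with the baseline to week-9 correlation that matches an SD of change of 6.5: 1 − 6.5²/(2 × 11.7²) = 0.846. The documents give no exclusion or arm-specific missingness rates, so those below are assumptions.

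**1. The plan's own figures.** A two-sample t-test with d = 5/6.5 needs 28 per group for 80% power. Power is 83.4% at 30 per group and 74.2% at 24 (30 less 20%). This reproduces the stated 28 and 74–83%. The 74% is therefore 24 patients per group with the full 5-point effect: attrition is treated as lost patients, not as zero changes.

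**2. Per-protocol selection, no true effect.** Suppose the least adherent fraction is excluded (a on MMFS, b on placebo) and adherence correlates ρ with change. With φ the normal density and z the normal quantile,

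bias = ρ × 6.5 × [φ(z_a)/(1−a) − φ(z_b)/(1−b)].

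- Equal exclusion: 0.
- 15% vs 10%: the bracket is 0.2743 − 0.1950 = 0.0793. Bias is 0.15 (ρ = 0.3) to 0.26 (ρ = 0.5). SE 1.795; two-sided error 5.1 to 5.2%.
- 25% vs 10%: the bracket is 0.4237 − 0.1950 = 0.2287. Bias is 0.45 to 0.74. SE = 6.5 × √(1/22.5 + 1/27) = 1.855; error 5.7 to 6.9%.
- 10% vs 25%: same size, opposite sign.

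**3. LOCF with a true 5-point effect, 20% missing per arm.** Expected difference: 0.8 × 5 = 4.0.

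| Method | LOCF | Observed scores only |
|---|---|---|
| t-test on change, power | 72% | 74% |
| ANCOVA (simulated), power | about 74% | about 76% |
| Estimate | 4.0 | 5.0 |

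The t-test LOCF figure uses variances 0.8 × 42.25 = 33.8 (placebo) and 33.8 + 0.8 × 0.2 × 25 = 37.8 (MMFS), so SE = √(71.6/30) = 1.545. Simulation runs varied by about one percentage point.

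**4. LOCF with no drug effect and unequal missingness.** If both arms change by c, bias = c × (placebo missing − MMFS missing).

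- c = 2, 30% MMFS vs 10% placebo missing: 2 × (0.1 − 0.3) = −0.4. Reversed: +0.4. Simulated ANCOVA error is about 5.5 to 5.9%.
- c = 0, the plan's placebo assumption: bias 0, error about 5%.
- ANCOVA on observed scores, same cases: bias about 0, error about 5%.

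The simulations in steps 3 and 4 take missingness as unrelated to outcome.

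**5. Cost of including non-adherent patients.** With the effect reduced to 5 × (1 − q):

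| Dilution q (assumed) | 30 scores per group | 24 scores per group |
|---|---|---|
| 10% | 75% | 65% |
| 20% | 65% | 55% |
| 30% | 54% | 45% |

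An undiluted per-protocol analysis with an assumed 21 per group would have 68%.

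**The case against.** The strongest reply is that the harm is assumed rather than shown. Intent-to-treat is already pre-specified. The milder exclusion scenario barely moves the error rate, and under the plan's own assumption of no placebo change LOCF does not inflate it. The change may also cost power: 55% in the 20% dilution case with 24 scores per group, against 68% for the undiluted per-protocol case. All of this stands. It limits the size of the point, but it does not make a post-randomisation subset a sound leading analysis.

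The lateness rule is also milder than the 5-day window suggests, because of the 10-day allowance. That allowance does not rescue a missed visit or compliance outside the range.

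Four stronger readings are tempting and are not supported:

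- **That the investigator judging deviations is unblinded.** Section 7.0 says "Until the trial is concluded, the randomization sequence will be blind to the study participants as well as research coordinators and raters" and does not list the investigator. But the Summary calls the trial double blind, and 11.8 keeps the blind until data lock and treats emergency unblinding as a decision for the principal investigator or another treating physician. What remains is narrower: nothing says that per-protocol membership is settled before unblinding.
- **That the per-protocol result favours MMFS.** The direction depends on which arm loses more patients, and the documents give no rates.
- **That LOCF costs appreciable power.** Compared by the same method, the difference is about 2 percentage points.
- **That an early-exit score could never be carried forward.** Section 9.1.2 speaks of end of study, and an exit MCCB is not forbidden. None is scheduled, however, and 8.1 places the assessment at 9 weeks.

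**Conclusion.** The point holds as one of ranking and imputation; an intent-to-treat analysis is planned. As written, the analysis that leads is per-protocol, it can discard patients with complete primary data, and the second analysis enters zero change for every missing week-9 MCCB score.

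The size of any per-protocol bias is unknown and may be zero. The 0.45 to 0.74 points and 5.7 to 6.9% error need 25% vs 10% exclusion and a correlation of 0.3 to 0.5. The LOCF effect on the estimate is clearer: one point of the planned five at 20% missing per arm. LOCF bias of about 0.4 points in either direction, with no drug effect, needs both a common 2-point change and 30% vs 10% missing. All figures take the plan's SD of change of 6.5. The LOCF point concerns the MCCB endpoints; it does not extend to the PANSS, which has a week-6 value. The plan should be changed, and the reason is validity.

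**What to change.** In 8.1:

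- Name one primary analysis for the working-memory endpoint: baseline-adjusted ANCOVA on all randomised patients who took any study compound, analysed as randomised, using every observed week-9 MCCB score regardless of adherence, interim attendance or deviations.
- Drop LOCF for the MCCB endpoints. As a sensitivity analysis, impute missing week-9 scores and shift the imputed MMFS scores downward in 1-point steps from 0 to 5. At 20% missing each step lowers the estimate by about 0.2 × 1 = 0.2 points, so the 5-point shift gives 5 − 1 = 4.0, the LOCF value. Imputation from arm and baseline alone adds nothing to the observed-score ANCOVA as a primary analysis: with one post-baseline score, both estimated 4.98 points in simulation.
- State that the week-9 MCCB will be sought from patients who stop study compound but allow follow-up (10.0).
- Keep per-protocol as a supportive analysis, with membership fixed and documented before unblinding.

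The cost is a few sentences and a few extra test sessions, plus the possible dilution tabulated above. Observed-score ANCOVA also assumes that missingness depends only on arm and baseline score; the shift analysis shows how far the result relies on that.

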#### **9.1.2 MATRICS Consensus Cognitive Battery (MCCB)**

The MCCB includes 10 tests that assess 7 cognitive domains: speed of processing, attention/vigilance, working memory, verbal learning, visual learning, reasoning and problem solving, and social cognition. The tests will be administered together in one 60-to 90-minute session. For subjects who use nicotine, the MCCB will be performed at least 30 minutes after nicotine intake. Though not strictly required by the protocol, whenever possible, the MCCB should be administered at the same time of day ( $\pm$  1 hour). The MCCB is a hybrid battery comprising multiple independently owned and published tests. Normative data for demographic corrections are derived from a single representative sample to which the tests were administered together as a unit, called "co-norming" [24]. The MCCB's high test-retest reliability makes it a sensitive and accurate measure of cognitive change, and its minimal practice effects ensure that it is appropriate for repeat testing [25]. The MCCB was developed by the National Institute of Mental Health (NIMH) MATRICS initiative. The MATRICS was designed to stimulate the development of psychopharmacological agents to improve cognition in schizophrenia. The selection of tests included in the MCCB involved a broad-based interdisciplinary consensus process that is described in more detail on the MATRICS website ([www.matrics.ucla.edu](http://www.matrics.ucla.edu)). Details of administration are included in the study-specific MCCB manual. The MCCB will be administered at baseline and end of study.

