#### **9.1.3 Positive and Negative Syndrome Scale (PANSS)**

The PANSS is an interview-based measure of the severity of psychopathology in adults with psychotic disorders. The measure is comprised of 30 items and 3 scales: the Positive scale assesses hallucinations, delusions, and related symptoms; the Negative scale assesses emotional withdrawal, lack of motivation, and similar symptoms; and the General Psychopathology scale addresses other symptoms such as anxiety, somatic concern, and disorientation. An anchored Likert scale from 1-7, where values of 2 and above indicate the presence of progressively more severe symptoms, is used to score each item. Individual items are then summed to determine scores for the 3 scales, as well as a total score. A Composite scale score (Positive scale score - Negative scale score) can also be calculated to show the relative valence of positive and negative symptoms. Total time required for the PANSS interview and scoring is approximately 30-40 minutes. PANSS raters will be required to meet specific training and education criteria before they are certified to rate for this study. In addition, raters will receive specific training and education regarding all the following assessments prior to study initiation. The PANSS will be administered at baseline, week 6, and end of study.

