#### **9.1.6 Clinical Global Impressions Scale (CGI)**

The Clinical Global Impressions (CGI) Severity and Change Scale will be used for repeated evaluations of global psychopathology. The CGI scale is widely used in schizophrenia research. The CGI-S is a single Likert scale rating severity of psychopathology on a scale of 1 (normal, not ill) to 7 (very severely ill). The CGI-C is a single Likert scale rating change of psychopathology during the trial on a scale of 1

C

(very much improved) to 7 (very much worse). The CGI will be completed at baseline and end of study.

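### In the intent-to-treat analysis, LOCF sets the MCCB change to exactly 0 for anyone without a week-9 test, and it gives no usable value for CGI-C

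*Combined protocol and SAP*

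**What the plan says.** Section 8.1 ranks a per-protocol analysis of completers first. It then adds: "Data will secondarily be analyzed for efficacy on an intent-to-treat basis", "with last observation carried forward (LOCF) for missing values or dropouts". The full analysis set leaves out only subjects who took no study compound. No post-baseline MCCB is required, so a treated dropout stays in.

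The measurement times are:

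- **MCCB.** Section 9.1.2: "The MCCB will be administered at baseline and end of study". The power paragraph of section 8.1 gives the same two times. Appendix 1 marks the extended battery, which includes the supplementary tests, on day 1 and at the final visit only.
- **BNSS.** Appendix 1 shows the same two marks.
- **CGI.** Section 9.1.6: "The CGI will be completed at baseline and end of study". The same section defines CGI-C as a rating of change over the trial.
- **PANSS.** Section 9.1.3: "The PANSS will be administered at baseline, week 6, and end of study".

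No MCCB or CGI-C is specified at early termination. Section 9.1.8 asks only for a final physical examination. Section 10.0 recognises subjects who stop treatment but allow follow-up.

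**The concern.** LOCF needs a post-baseline observation to carry. For the MCCB, the supplementary tests and the BNSS there is none between baseline and week 9, so the rule becomes baseline carried forward. PANSS is the exception, for subjects who reach week 6. For CGI-C, which section 3.0 names as the secondary efficacy endpoint, there is no earlier rating of change to carry.

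Among the section 8.1 efficacy analyses, this is the only one that keeps dropouts, so it is the check on whether the per-protocol result depends on who completed. As written, its estimate moves mechanically with the active-arm dropout rate, and a reader could take that attenuation for lack of robustness. The plan does not say which effect the analysis targets, so it is unclear whether the shift is intended. The imputed zeros also enter the model as if they had been observed.

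**Working it through.** **Inputs (section 8.1).** Mean change 0 on placebo and 5 on active; SD of change 6.5; baseline SD 11.7; two-sided alpha 0.05; 30 per arm; attrition up to 20%. The split of dropout by arm is not given. Unequal splits and any placebo gain below are assumptions.

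**1. The plan's own figures.** A two-sample t-test with effect size 5/6.5 = 0.769 needs 27.5, so 28 per group. Power is 83.4% at 30 per group and 74.2% at 24 (30 less 20%). This matches the stated 28 per group and 74–83%.

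**2. Expected LOCF difference.** Let pA and pP be the shares without a week-9 MCCB, δ the treatment effect and g a gain common to both arms, with dropout unrelated to outcome:

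E(difference) = (1 − pA)(g + δ) − (1 − pP)g = δ(1 − pA) + g(pP − pA).

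With g = 0 and δ = 5:

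- 10% per arm: 5 × 0.9 = 4.5
- 20% per arm: 5 × 0.8 = 4.0
- 30% active, 10% placebo: 5 × 0.7 = 3.5

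**3. Why the SE shrinks (20% per arm).** The variance of change is 0.8 × (6.5² + 5²) − 4² = 37.8 on active and 0.8 × 6.5² = 33.8 on placebo. The pooled SD is √35.8 = 5.98, below 6.5, while n is still counted as 30 per arm. Power of a t-test on change scores is 72%.

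**4. Planned ANCOVA, by simulation.** There were 6,000 runs per scenario with fixed dropout counts. The correlation implied by the two SDs is ρ = 1 − 6.5²/(2 × 11.7²) = 0.846. True effect 5, g = 0:

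| Dropout (active / placebo) | LOCF estimate | LOCF coverage of 5 | LOCF power | Observed-case power |
|---|---|---|---|---|
| 10% / 10% | 4.49 | 94.0% | 80.2% | 81.0% |
| 20% / 20% | 4.04 | 90.6% | 75.8% | 77.2% |
| 30% / 10% (assumed) | 3.48 | 83.9% | 62.0% | 76.2% |

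At 20% per arm:

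- LOCF: model SE 1.51, empirical SD 1.48.
- Observed-case ANCOVA: estimate 5.05, SE 1.82, coverage 95.2%.
- Complete data on all 60: SE 1.62, power 85.9%.

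The LOCF SE matches the estimator's own spread, and coverage of its own mean is 96.0%. Coverage of 5 is therefore lost through the shift in the estimate, not through a separate variance error.

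**5. With the plan's stated correlation of 0.5.** With SD 11.7, this implies an SD of change of √(2 × 11.7² × 0.5) = 11.7, which conflicts with 6.5. Coverage of 5 is then 93.5% at 20% per arm and 90.7% at 30% active / 10% placebo.

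**6. If dropouts lose all benefit (20% per arm).** The target is 0.8 × 5 = 4.0.

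- LOCF: estimate 3.99, SE 1.51, coverage of 4.0 95.3%, power 74.6%.
- All 60 actually tested: estimate 3.99, SE 1.66, power 65.2%.
- Observed-case ANCOVA: estimate 4.99, coverage of 4.0 91.3%.

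**7. Type I error.** Without drift, the LOCF rejection rate is 5.1% (20% per arm) and 4.6% (30% / 10% split). With an assumed 3-point gain in both arms and an assumed 30% placebo / 10% active dropout, the formula gives a false benefit of 3 × (0.3 − 0.1) = 0.6. The simulation gives 0.61, with rejection 6.4%.

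**8. Responders (gain of at least 5).** Placebo: 1 − Φ(5/6.5) = 22.1%. Active: 50.0%. With 20% set to non-response these become 17.7% and 40.0%, and the gap falls from 27.9 to 22.3 percentage points.

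**The case against.** The strongest reply is that little is at stake. LOCF touches only the second-ranked analysis. At the plan's own ceiling, split equally, power is 76% against 77% and type I error is about 5%. With no placebo change the distortion is toward no effect. All of that stands and limits the weight of the point.

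The larger figures need assumptions that the documents do not supply. Coverage of 84% needs 30% against 10% dropout, while section 8.1 speaks only of "allowing for attrition up to 20"%. The 6.4% type I error also needs a 3-point gain in both arms. The plan does not expect one: section 8.1 assumes no placebo improvement, and section 9.1.2 says of the MCCB that "its minimal practice effects ensure that it is appropriate for repeat testing". With ρ = 0.5, coverage at 20% per arm is near nominal. These points also stand.

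The loss of coverage depends on the target. If dropouts are taken to lose the benefit, LOCF reaches the right value. It does so only because the assumed placebo change is zero, and its SE is still smaller than with everyone tested.

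An MCCB done at an early final visit could be carried forward, and Appendix 1 marks CGI-S/C on day 1. No early MCCB is scheduled for dropouts, however, and a day-1 CGI-C entry would precede any change to rate.

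Finally, observed-case ANCOVA also leaves out subjects without week-9 data, and it overstates the effect if dropouts lose benefit. That is correct, and it is why a placebo-based sensitivity analysis belongs beside it. Observed-case ANCOVA still differs from the per-protocol analysis: it keeps subjects with a week-9 score who fail the compliance, visit-window or deviation criteria.

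**Conclusion.** The concern holds. Followed as written, the rule assigns zero change and non-response to every treated subject without a follow-up MCCB, and it supplies no meaningful CGI-C value. If the target is the effect had everyone stayed on treatment, the estimate falls from 5.0 to 4.0 at 20% dropout per arm, with 91% coverage. If the target allows for lost benefit, 4.0 is right under the zero-placebo-change assumption, but the SE of 1.51 is smaller than the 1.66 that full testing would give. These figures rest on the plan's means, the SD of change of 6.5 and dropout fixed independently of outcome. The harsher scenarios rest on assumed unequal dropout or drift.

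The point should be fixed, but it does not threaten the first-ranked analysis. A subject who stops treatment but attends week 9 has a real score and is not affected.

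**What to change.** 1. State which effect the intent-to-treat analysis is meant to estimate.
2. For the MCCB endpoints, supplementary tests, BNSS and CGI-C, replace LOCF with an analysis valid under missing at random. This can be baseline-adjusted ANCOVA on all observed week-9 values, or multiple imputation by arm from the baseline score and any available PANSS. For CGI-C, use baseline CGI-S and PANSS.
3. Add placebo-based imputation as a sensitivity analysis for the case where dropouts lose the benefit.
4. If missing is to count as non-response in the responder analysis, declare it as a deliberate convention.
5. Use the scheduled week-9 MCCB from subjects who stop treatment but permit follow-up.

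The cost is SAP wording and a little programming, with no extra visits or patients. Intervals widen. At 20% dropout per arm the SE is 1.82 for observed-case ANCOVA and 1.87 for multiple imputation by arm from baseline (1,500 runs, 20 imputations; estimate 5.08, coverage 96.5%, power 75.1%), against 1.51 under LOCF. In the same runs the placebo-based analysis estimates 4.05 with SE 1.91 and about 56% power. Early dropouts have no week-6 PANSS, so multiple imputation may add little beyond observed-case ANCOVA.
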